7 RECRUITMENT

Participants will be recruited in Spain, United Kingdom and Italy according to legal requirements in each country. Also, we will obtain the committee approbation in the hospitals, as well as, doing a contract in each hospital. The administrative matters will be handled by CRO Business&Decision Life Sciences (Contract Research Organization).

7.1 INFORMED CONSENT AND ELEGIBILITY CRITERIA

Potential participants will be evaluated by authorized members of the clinical trial who will be trained to provide the necessary information to adequately explain the trial protocol and solve the issues that arise from the possible candidate to join the study team. If necessary, several members of the research team should discuss and solve the doubts concerns of the patient.

The team member will be willing to answer questions from potential participants verbally or in writing if necessary in simple, clear and understandable language. Upon acceptance by the participant, potential eligibility criteria shall be formally evaluated, if they do, he or she shall sign the informed consent (Annex 1)

The Principal Investigator (PI) will have overall responsibility for solving any problems that might arise about informed consent and supervise all study participants to ensure that everyone involved in this process are properly trained according to the ethics committee approval protocol and Guides of Good Clinical Practice (GCP) and the Declaration of Helsinki of 1996.

Informed consent will be obtained before the participant is assessed by specialists with the purposes of the study. The right of a participant to refuse to participate without giving reasons will be respected. The participant may withdraw at any time without giving reasons and without prejudice to his / her further treatment. At no time during the process of obtaining informed consent the investigator or any member of the research team coerce or influence for the patient to be part of the clinical trial.

The investigator will check if the participant has successfully completed the consent form and that it has been signed and dated correctly. The researcher must sign and date the form in the right area on the same date as the participant. The original informed consent will be filed in the archive of the researcher.

If a participant is ineligible after randomization, it shall be reported immediately to the principal investigator.

Patients who during the follow up present a moderate or severe cognitive impairment will remain in the group assigned.

7.2 RANDOMIZATION

After verification that the participant fulfils the eligibility criteria and signed the informed consent, allocation will be made to a control or/an intervention group.

Participants will be randomized 1:1 through the eCRF by Linkcare Company, which also will do the database.

Patient's participation in the study and the telephone number of the study contacts will always be registered in his/her clinical record.

According to the study's schedule, the intervention phase will start the sixteenth week, taking into account the adjustments of the ethics committee in each country. Follow-up will be made at hospital discharge and at the third and sixth month after discharge.

7.3 SAMPLE SIZE

Dependence and disability affects quality of life perception and increases health costs. Hence, this variable will be taken to calculate sample size. According to literature, the incidence of disability in frail older people is approximately 40%.

In order to avoid the estimation bias, the sample size will have at least 10 outcomes as variables. Therefore, the formula has been calculated for a 95% confidence interval to obtain at least 40 events.

$$n * p \pm z_{1-\frac{\alpha}{2}} \sqrt{n * p * (1-p)}$$

It has been assumed drop-out rate of 20% and an incidence of disability described above. Hence, the sample size should be at least 1860 participants. In each clinical setting (emergency room, general surgery, oncology, cardiology and nephrology) 310 participants should be evaluated (155 in each group: control and intervention).

In case of not obtaining the minimal sample size in each clinical setting, the pondeate models will be made. Additionally, a meta-analysis will be performed including the global effect of the intervention according to clinical setting and with a thorough sensitivity analysis.

7.4 STATISTICAL ANALYSIS

Firstly, subject's basal characteristics at recruitment will be analyzed. Descriptive statistics of epidemiological and clinical data will be calculated (described in section 9). This analysis will be done in a conjoint manner, according to treatment and clinical setting (emergency room, general surgery, oncology, cardiology, and nephrology).

To verify the differences between the arms of the study a Mann-Whitney test will be made. Based on the inclusion criteria, it is expected that the differences will be produced by the intervention, and not because of differences between groups.

[figure not shown]
To evaluate the intervention in each clinical setting, the effect of the intervention and its statistical significance will be determined.

These effects shall be broken down into two classes depending on the event. First the prevalence rate, and in case the event's duration could be assessed, evaluate if this duration has changed..

For each outcome described in section 4, comparisons between predictive values of the logistic models for each scale will be made in order to determine which scale is optimal in a global manner, according to clinical setting.

In case the date of death and hospitalization can be obtained, survival models will be done.

Diagram 1. Flowchart of randomized clinical trial

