9 ASSESSMENTS DURING THE STUDY

9.1 BASELINE EVALUATION (visit 0= FIRST VISIT)

After the inclusion of a participant in the study, a comprehensive geriatric assessment will be done with the following parts:

Demographics and epidemiology: Date of birth, age, sex, race, caregiver, marital status, number of persons in the house, and, number of hospitalization in the last year, follow up by others specialist, level of education.

- Medical history

Personal Medical and Surgery History should be recorded in the electronic Case Report Form (eCRF).

- Medications:

In the CRF we register all the regularly medication use (previous hospitalization)

- Functional status

Evaluate functional status with the following scales: Barthel Index, Lawton Index, measures based in performance (SPPB-Short Physical Performance Battery) and PASE Scale, Annex 2.

- Cognitive and depression:

Evaluate the results with MMSE and Geriatric Depression Scale GDS, and delirium risk with CAM scale. See Index 2.

- Physical examination:

Vital signs and physical examination as usual by the clinical investigator.

- Geriatric Syndromes Assessment:

Immobility: Falls and imbalance.

Incontinence: urinary and fecal.

Sensory deprivation

Iatrogenic: Record the numbers of falls during the hospitalization and adverse effects

Pain: assess pain using the VAS Scale. Nutritional Status:

Performed screening for nutritional status using the scale MNA (Mini Nutritional Assessment), Index 2.

- Comorbidities:

Comorbidities will be quantified by Charlson Index, Index 2.

Quality of Life :

The evaluation for the quality of life using the EuroQol five-dimensional (EQ-5D), Index 2.

Caregiver :

- Assessment for the burden of the caregiver; Will be evaluated with The Modified Caregiver Strain Scale. Index 2.

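### Free improvement: the only between-arm test named in section 7.4 is an unadjusted Mann-Whitney test; a regression on the baseline score already recorded would gain precision and give an effect estimate

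*Combined protocol and SAP*

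**What the plan says.** After a paragraph on describing patients at recruitment, section 7.4 states: "To verify the differences between the arms of the study a Mann-Whitney test will be made". It names no outcome, time point, covariate or estimate. The next sentence reads: "Based on the inclusion criteria, it is expected that the differences will be produced by the intervention, and not because of differences between groups".

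A separate paragraph then promises: "To evaluate the intervention in each clinical setting, the effect of the intervention and its statistical significance will be determined". No method is attached. Section 7.3 adds that "a meta-analysis will be performed including the global effect of the intervention according to clinical setting and with a thorough sensitivity analysis" and, for settings that recruit too few, that "In case of not obtaining the minimal sample size in each clinical setting, the pondeate models will be made".

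The other models do not fill the gap:
- Logistic models are there to rank scales: "comparisons between predictive values of the logistic models for each scale will be made in order to determine which scale is optimal".
- Survival models depend on dates being available and have no stated covariates.
- Centre and country appear only in section 10, in an optional cost model.

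The covariates are collected. For the first visit, section 9.1 says: "Evaluate functional status with the following scales: Barthel Index, Lawton Index", and it adds SPPB and PASE. Sections 9.3 and 9.4 repeat Barthel, Lawton and PASE by telephone at 3 and 12 months. Section 4.1 lists all three among the primary outcomes.

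**The concern.** In frail inpatients, later function is likely to follow entry function closely. Entry Barthel can run from 40 to 100, because only scores below 40 are excluded. A test that sees only the follow-up score leaves that variation in the noise, and this matters most within a setting, where the plan has 155 patients per arm before dropout. A rank test with no accompanying estimate also gives only a P value, while section 7.4 promises an effect for each setting.

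The stated reason for attributing differences to the intervention is also wrong. Shared eligibility makes patients alike in kind; it does not make the arms comparable. Randomisation does that, on average. Section 7.2 gives 1:1 allocation and mentions no stratification by setting or centre.

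**Working it through.** **1. The plan's own figure.** Section 7.3 wants at least 40 events at the lower 95% limit, with incidence p = 0.40 and 20% dropout.
- Solve n·p − 1.96·√(n·p·(1−p)) = 40. This gives n = 127.06, rounded up to 128.
- 128 × 1.2 = 153.6, so 154 per arm against the stated 155. The figure reproduces.
- Evaluable patients per arm per setting: 155 × 0.8 = 124.

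This calculation contains no effect size, power or test, so it does not show how any arm comparison performs.

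**2. Assumptions for the comparison.** The documents give no SD, effect size or baseline-to-follow-up correlation (ρ). Assumed: Barthel in steps of 5, mean 75, SD 20, entry score at least 40; shift d = 0.30 SD (0.30 × 20 = 6 points); ρ from 0.3 to 0.7; two-sided 5% level.

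**3. Closed form, ignoring rounding and the ceiling.**
- Comparison of means: z = d·√(n/2) = 0.30 × √62 = 2.36.
- Mann-Whitney under normality: multiply by √(3/π) = 0.977, giving 2.31. Power = Φ(2.31 − 1.96) = 64%.
- Baseline-adjusted: divide 2.36 by √(1−ρ²).

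| ρ | adjusted z | power, closed form | power, simulated | fewer patients needed than an unadjusted comparison of means (ρ²) |
|---|---|---|---|---|
| 0.3 | 2.48 | 70% | 65% | 9% |
| 0.5 | 2.73 | 78% | 74% | 25% |
| 0.6 | 2.95 | 84% | 81% | 36% |
| 0.7 | 3.31 | 91% | 87% | 49% |

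The simulated column uses the bounded, stepped Barthel score with 2,000 runs; Mann-Whitney power there is about 62%. The ceiling lowers both methods slightly. The result at ρ = 0.3 is the least certain in relative terms: another run gave 61% against 67%.

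**4. A different shift.** Take d = 0.356 SD, which gives an unadjusted comparison of means 80% power at 124 per arm. Mann-Whitney then has about 78%, and the adjusted analysis 84%, 90% and 97.5% at ρ = 0.3, 0.5 and 0.7.

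**5. Validity.** With no true effect, both methods reject in about 5% to 6% of simulated trials.

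**6. Chance imbalance.**
- Per setting, the SD of the standardised baseline difference is √(2/124) = 0.127, so its 95% range is ±0.25.
- Over the whole trial, 1860 × 0.8 / 2 = 744 per arm; √(2/744) = 0.052, so the range is ±0.10.
- Among simulated null trials beyond the per-setting range, Mann-Whitney rejected in about 11%, 17% and 26% (ρ = 0.3, 0.5, 0.7), against about 4% to 7% for the adjusted analysis. By construction these are about 5% of trials, and the overall rate in step 5 already includes them.

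**7. The baseline-check reading.** The sentence follows the description of patients at recruitment, and the next one contrasts the intervention with differences between groups. On that reading the test asks whether randomised arms differ other than by chance, which is already known. Section 7.4 then names no arm comparison that uses the baseline score.

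**The case against.** The strongest reply is that an unadjusted rank test is valid under randomisation and suits a bounded, skewed scale. That stands: the gain is in efficiency and estimation, and at ρ = 0.3 it is only a few points.

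Three stronger readings are tempting, and the documents do not support them:
- **Setting is ignored.** It is not. Section 7.4 determines effects within each setting and section 7.3 combines them by meta-analysis, which is a stratified approach. A single Mann-Whitney test pooled over settings is not clearly planned.
- **Chance imbalance biases the primary results.** It does not inflate the overall type I error. It adds variance, and it misleads only conditionally on an unlucky draw.
- **Mann-Whitney is definitely the primary outcome test.** The text does not say, and a baseline check is at least as natural a reading. The remedy is the same on either reading.

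Other objections stand in part. Section 7.3 sizes the trial on a binary disability event, and the power figures above, for a shift in a score, do not carry over to it. Its target of 40 events at 10 per variable (40 / 10 = 4) may hint at multivariable models, but no covariate is named. If five settings at 124 per arm (620) were pooled at the same 0.30 SD shift, Mann-Whitney power would be Φ(0.30 × √(310 × 3/π) − 1.96) = 99.9%, so at that shift the loss matters within settings. Finally, baseline adjustment does not settle how deaths before follow-up are handled.

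**Conclusion.** The point holds as a free improvement, not as an error that invalidates the analysis. Section 7.4 names one unadjusted test without an outcome or time point, rests attribution on the wrong ground, and leaves the recorded baseline scores unused in every clinical-outcome comparison. Under the assumed Barthel distribution and a 0.30 SD shift, adjustment gains about 3 points of power per setting at correlation 0.3 (65 − 62) and about 25 at 0.7 (87 − 62). The direction is secure at any appreciable correlation. The size depends on an SD, a shift and a correlation that the documents do not give. SPPB falls outside the point, because Table 2 schedules it only at the initial visit.

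**What to change.** In section 7.4:
1. Name the outcome and time point for each arm comparison. Section 7.2 and section 9 differ on the last follow-up (six or 12 months after discharge) and must be reconciled first.
2. Within each setting, regress the follow-up Barthel, Lawton and PASE score on arm, the baseline value of the same scale, and centre. Use proportional odds if the ceiling is marked. Report the adjusted difference with its 95% CI (for proportional odds, the adjusted odds ratio with its 95% CI).
3. Combine the setting estimates in the meta-analysis already planned in section 7.3, or fit one model with setting and an arm-by-setting term, so that the per-setting effects are kept.
4. If disability is analysed as a binary event, use logistic regression with the same baseline covariate.
5. Keep a setting-stratified rank test as a sensitivity analysis, and state how deaths before follow-up enter the analysis.
6. Replace the sentence that relies on the inclusion criteria with a reference to randomisation. Describe baseline characteristics by arm without testing them.

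The cost is analysis wording. The covariates are already scheduled, so no patient, visit or measurement is added.

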4 OUTCOMES

4.1 PRIMARY OUTCOMES:

1. **Disability:** It was measured by the Barthel Index for basic Activities of Daily Living and the Lawton index for instrumental activities of daily living.
2. **Functional status and performance-based measures:** Functional status and performance-based measures: Is measured by Short Physical Performance Battery (SPPB), Physical Activity Scale for the Elderly (PASE SCALE).
3. **Quality of Life:** Quality of life was assessed by self-reported questionnaire EuroQL 5D 5L. It will be measured during admission to hospital and follow-up.
4. **Geriatrician Intervention:** The impact of their intervention is measured by quantifying in a register any additional tests requested and medical advice by other specialists.

4.2 SECONDARY OUTCOMES:

Prevalence of Delirium: The delirium cases are detected by Confusion Assessment Method (CAM) scale.

Cognitive Impairment: Will be measured by the Mini Mental State Examination (MMSE) in the initial assessment.

Depression: will be assessed using the Geriatric Depression Scale in the baseline assessment.

Health-care associated infections: Acquired during hospitalization start.

Geriatric Syndromes: The geriatric evaluation including the following aspects: clinical, functional, mental and social.

Comorbidity: Will measured at initial assessment thorough Charlson index

Nutritional Status: Will measured at initial assessment thorough the Mini Nutritional Assessment and body Mass index.

Polypharmacy: Defined as five or more prescription drugs.

Mortality rate: Number of deaths during follow-up. It is calculated using official report of the National Statistics Institute (INE).

Average stay hospitalization: Average length of stay of stay all discharges. We will obtain from Hospital Admissions service.

Hospitalization Rate in Emergency room: Number of hospital admissions over the total of patients admitted in the hospital.

Readmission rates: Number of readmissions during of follow-up period. I will get the data in Hospital Admissions Service.

Institutionalization: Number of patients referred to nursing home after discharge or at any time during follow-up. This information is obtained directly from patients or their relatives.

Requirement of caregiver: Number of patients who require a caregiver after hospital discharge.

Caregiver burden: Will be used Zarit Scale for assessing caregiver burden

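### Four unranked primary outcomes and significance sought in every clinical setting, with no deciding outcome, visit, tied test or multiplicity rule

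*Combined protocol and SAP*

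**What the plan says.** **Primary outcomes (4.1).** There are four, in no stated order of importance.

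- Disability: "It was measured by the Barthel Index for basic Activities of Daily Living and the Lawton index for instrumental activities of daily living".
- Functional status, by SPPB and PASE.
- Quality of life, by EQ-5D-5L.
- A register of additional tests and specialist advice.

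None has a primary visit or an endpoint form (mean, change or event).

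**Effectiveness analysis (7.4).** The central sentence is "To evaluate the intervention in each clinical setting, the effect of the intervention and its statistical significance will be determined". The methods around it are:

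- "To verify the differences between the arms of the study a Mann-Whitney test will be made";
- effects divided into prevalence and, where it can be assessed, duration;
- "comparisons between predictive values of the logistic models for each scale will be made in order to determine which scale is optimal";
- "In case the date of death and hospitalization can be obtained, survival models will be done".

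**Sample size (7.3).** Of dependence and disability the section says "Hence, this variable will be taken to calculate sample size", and it takes from the literature that "the incidence of disability in frail older people is approximately 40" per cent. It asks for 310 participants per setting (155 per arm) and 1860 in total, with 20% dropout. On pooling it says: "Additionally, a meta-analysis will be performed including the global effect of the intervention according to clinical setting and with a thorough sensitivity analysis".

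**Economic evaluation (10).** The cost-effectiveness text states that the study's primary outcomes will be the between-group difference in functional status.

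**The concern.** A confirmatory trial needs one result, named in advance, that settles whether the intervention works. Here a reader cannot tell which result that is. Effectiveness could be claimed from whichever scale, visit or setting turned out significant, and such a result could not be read at its nominal error rate.

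The opposite error is also open. Each setting holds about a fifth or a sixth of the patients, so a real effect common to all settings could be significant in some and not in others. That pattern could be taken for a difference between settings when there is none.

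Neither problem can be repaired convincingly once the data have been seen.

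**Working it through.** **1. What the plan's sample size is.** Section 7.3 requires the lower 95% limit of the event count to reach 40, that is n·p − z·√(n·p·(1−p)) ≥ 40 with p = 0.40 and z = 1.96.

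- n = 127: 50.8 − 1.96·√30.48 = 39.98, too small.
- n = 128: 51.2 − 1.96·√30.72 = 40.34, sufficient.
- Adding 20%: 128 × 1.2 = 153.6, so 154, close to the stated 155.

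The figure is therefore a precision target within one arm. It contains no between-arm difference, test level or power, so the sample size does not reveal a deciding comparison.

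**2. Can a deciding analysis be found elsewhere?**

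- *Outcome.* 7.3 points to disability, which has two scales and no event definition. The only Barthel cut-off is the exclusion limit in 6.2. Section 10 points to functional status, which in 4.1 is a different primary outcome (SPPB and PASE). Section 9.1 uses that term for all four functional scales, but that reading does not select one either.
- *Visit.* 7.2 gives discharge, 3 and 6 months; 9.2–9.5 and Table 2 give discharge, 3 and 12 months. None is called primary.
- *Test.* The Mann-Whitney test is tied to no outcome or visit. It follows the description of baseline characteristics but can also be read as the arm comparison. The logistic models choose between scales, the survival models depend on dates being available, and the GLM and multilevel models in section 10 are for costs.
- *Multiplicity.* No rule appears anywhere.
- *Number of settings.* 7.3 and 7.4 name five. Table 1 has six if elective and emergency surgery are counted separately. 6 × 310 = 1860, whereas 5 × 310 = 1550.

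**3. False positives.** Assume 0.05 per test, one visit, independent tests, and that any positive would be claimed. The chance of at least one false positive in m tests is 1 − 0.95^m.

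| Scales tested | Five settings | Six settings |
|---|---|---|
| One | m = 5: 23% | m = 6: 26% |
| Two (Barthel, Lawton) | m = 10: 40% | m = 12: 46% |
| Four (Barthel, Lawton, PASE, EQ-5D) | m = 20: 64% | m = 24: 71% |

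Correlation between scales within a setting lowers these. At an assumed correlation of 0.7, simulation gives 35% for two scales and 50% for four over five settings. Testing at several visits would raise them.

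**4. What one setting can detect.** Inputs from 7.3: control incidence 0.40, and 155 × 0.8 = 124 per arm after dropout. Assumed: two-sided 0.05 and 80% power. With p̄ the mean of the two rates and q = 1 − p,

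power = Φ{ [ |p1 − p2|·√n − 1.96·√(2·p̄·(1 − p̄)) ] / √(p1·q1 + p2·q2) }.

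- One setting, n = 124 per arm: 80% power at 40% against 23.5%, a difference of 16.5 points.
- Five settings pooled, n = 5 × 124 = 620 per arm: 80% power at 40% against 32.4%, a difference of 7.6 points.

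**5. How often the settings would disagree by chance.** Suppose the same true reduction in all five settings. With per-setting power w, the chance that one to four are significant is 1 − (1 − w)^5 − w^5.

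| Assumed reduction | Power per setting | One to four of five significant |
|---|---|---|
| 5 points | 13% | 49% |
| 10 points | 38% | 90% |
| 15 points | 72% | 81% |
| 20 points | 93% | 29% |

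For the 10-point case: 1 − 0.622^5 − 0.378^5 = 1 − 0.093 − 0.008 = 0.899. Pooled power at 10 points with 620 per arm is 96%.

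**The case against.** The best defence is that the plan is loosely written rather than empty. Disability is listed first in 4.1 and is the sizing variable in 7.3. Section 7.4 names a test for differences between the arms, and its next sentence expects those differences to come from the intervention. It also gives an effect measure, prevalence then duration. A pooled analysis across settings is already planned in 7.3.

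Much of this stands, and it limits what can be said:

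- A reader might infer that the plan names no test at all. It does name methods; none is tied to a primary outcome and visit.
- A reader might take 64% as the plan's false-positive rate. The documents state neither a per-test level nor that one positive result counts as success, so the percentages illustrate a risk.
- A reader might infer that the plan's own figures predict conflicting settings. The plan gives 40% incidence and the group sizes but no between-arm difference. The chance of a mixed picture runs from 29% to 90% over the effects shown, so the 90% should not be quoted alone.
- A reader might add the lack of baseline adjustment as a flaw. An unadjusted comparison is valid under 1:1 randomisation, and section 10 already measures benefit as change from baseline. Any gain in precision depends on correlations that the documents do not give.

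The defence does not supply the missing choice. Disability remains two scales without an event or visit, section 10 names another domain, and the meta-analysis is introduced as an addition.

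**Conclusion.** The concern holds in this form: the plan has no single pre-named outcome, visit, tied test and multiplicity rule, while it seeks significance setting by setting. This affects the main effectiveness conclusion and should be settled before any outcome data are examined by arm.

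The absence of a rule and the conflicting pointers are read directly from the documents. The sizes are illustrations. The error rates of 23%, 40% and 64% assume 0.05 per test, independence and a claim on any positive. The detectable differences use 7.3's incidence and dropout but assume 80% power and two-sided 0.05, and they apply to a binary event rather than to a continuous Barthel score. The mixed-result figures also assume a uniform effect. The study flowchart in 7.4 was not available to check.

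**What to change.** **In 7.4, name one primary test.**

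- One scale at one stated visit. Barthel is suggested because it is the only functional scale scheduled at baseline, discharge, 3 and 12 months (9.1–9.4). Another single named scale would also cure the defect.
- Choose the visit after reconciling 7.2 (3 and 6 months) with 9.3–9.5 (3 and 12 months).
- Analyse all randomised patients by assigned arm, pooled over settings, at two-sided 0.05, in a regression adjusted for the baseline value, setting and centre. Say whether this is the 7.3 meta-analysis or whether that is supportive.
- If the binary disability of 7.3 is kept, define the event and its threshold.
- State in advance how deaths enter the scale, since no rule exists now.

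**Place everything else.**

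- Make Lawton, SPPB, PASE, EQ-5D and the register secondary, in a stated order or labelled descriptive. SPPB is absent from the assessment lists in 9.2–9.4, and Table 2 is ambiguous about it after baseline, so its post-baseline measurement needs confirming.
- Reconcile the section 10 statement on primary outcomes with the choice made, and five settings with six.
- Report per-setting effects as estimates with confidence intervals, plus a treatment-by-setting interaction, without separate significance claims.

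**Cost.** This is mainly wording and a standard regression. Barthel at the scheduled visits, setting, centre and deaths are already recorded; a six-month primary visit would need an added Barthel assessment. The claim would rest on one scale and one pooled effect, which can hide real differences between settings. Per-setting significance claims are given up, and the chosen rule for deaths may reduce power.

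### The only unconditional outcome model named in section 7.4 ranks scales by predictive value; it does not estimate the arm effect, and 'scale' is left undefined

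*Combined protocol and SAP*

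**What the plan says.** After the descriptive statistics, section 7.4 contains five analysis elements:

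- A between-arm test: "To verify the differences between the arms of the study a Mann-Whitney test will be made". It follows the baseline descriptives and names no outcome.
- An intention for each clinical setting: "the effect of the intervention and its statistical significance will be determined".
- A split of effects into two classes: "First the prevalence rate, and in case the event's duration could be assessed, evaluate if this duration has changed". No model is attached to either class.
- For the section 4 outcomes, "comparisons between predictive values of the logistic models for each scale will be made in order to determine which scale is optimal", to be done "in a global manner, according to clinical setting".
- A conditional plan: "In case the date of death and hospitalization can be obtained, survival models will be done".

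Section 4.1 gives the disability outcome two instruments: "It was measured by the Barthel Index for basic Activities of Daily Living and the Lawton index for instrumental activities of daily living". Functional status also has two, SPPB and PASE. Section 7.3 adds weighted models if a setting falls short of its sample size, and a meta-analysis of the intervention effect by setting. Section 10 names regression models for costs. Nowhere do the documents specify a model with treatment arm as a term for a section 4.1 outcome.

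**The concern.** Predictive value describes how well a model classifies patients. It is not a contrast between randomised groups, so the one model named unconditionally for the outcomes does not answer the trial's question about effectiveness.

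The second difficulty is the undefined word 'scale'. If it refers to outcome instruments, the measure that represents disability could be settled after the data are in. Depending on how the closing phrase of that sentence is read, the choice could also differ between settings, and the section 7.3 meta-analysis could then combine effects on different scales. At stake are the false-positive rate of the disability comparison and the meaning of the pooled estimate.

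**Working it through.** **Does the plan's own arithmetic supply an arm contrast?** The plan gives no figure for this step. Its sample size can be approximately reproduced. The smallest n with n·p − 1.96·√(n·p·(1−p)) ≥ 40 at p = 0.40 is 128, since 51.2 − 1.96 × 5.54 = 40.3. Adding 20% gives 128 × 1.2 ≈ 154, against 155 stated per arm and setting. This is the precision of a single proportion. It contains no arm difference, power or significance level for a comparison, so section 7.3 does not define the effect that section 7.4 leaves open.

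**Which scales could compete?** From sections 9.1 to 9.4:

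| Scale | Baseline | Discharge | 3 months | 12 months |
|---|---|---|---|---|
| Barthel | yes | yes | yes | yes |
| Lawton | yes | no | yes | yes |
| PASE | yes | no | yes | yes |
| SPPB | yes | no | no | no |

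The two follow-up contacts are by telephone. Table 2 names SPPB individually only in the initial-visit cell. After baseline, disability is therefore the only section 4.1 domain with two competing scales, and only at the follow-up calls.

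**Upper bound for a choice between two scales.** Inputs: two standard normal test statistics under no arm effect, a two-sided 5% level (assumed, as the plan states none for comparisons), and selection of whichever shows the larger arm difference. The per-setting rate is f = P(max(|Z₁|, |Z₂|) > 1.96), from 400,000 simulated draws. Over five settings treated as independent, the chance of at least one false positive is 1 − (1 − f)⁵. The correlation is not in the documents, so a range is shown.

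| Correlation (assumed) | f per setting | Five settings |
|---|---|---|
| 0 | 9.7% | 40% |
| 0.5 | 9.1% | 38% |
| 0.7 | 8.4% | 35% |
| 0.9 | 7.1% | 31% |

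At 0.5: 1 − 0.9091⁵ = 1 − 0.621 = 0.379. The reference without any scale choice is 1 − 0.95⁵ = 0.226. The part due to choosing the scale is about 4 percentage points per setting and about 15 over five settings (37.9 − 22.6).

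**Under the rule as written.** Selection is on predictive value, and the text mentions no arm term. If the models leave arm out, the choice has little or no connection with the arm difference, and inflation is smaller than shown or absent. Section 7.4 does not say that arm is left out, so the table is a ceiling and not an estimate.

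**The case against.** The best counter-argument is that the sentence concerns predictors. Predictive values of logistic models for each scale is how one would describe comparing frailty tools. Section 4 also includes mortality, readmission and institutionalisation, which have no rival scales to choose between. Fried's criteria and the FRAIL scale are both used in the trial, and section 2.2 lists frailty assessment tools among the topics of the observational phase. On that reading no outcome is selected and the false-positive figures fall away. The documents do not settle the matter, so this reading stands as a real possibility. It leaves untouched the observation that the step is not an arm comparison.

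Several stronger readings are tempting and are not supported:

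- *That this is the only outcome model, or that no arm comparison is planned.* Survival models are planned conditionally. The section also announces an intervention effect with its significance, and names a Mann-Whitney test between arms. These are underspecified but not absent.
- *That four scales compete*, giving 1 − 0.95⁴ = 18.5% per setting and 1 − 0.95²⁰ = 64% over five settings. The step works outcome by outcome, and SPPB is not listed after baseline.
- *That the p-value is necessarily invalid.* That needs selection linked to the arm difference, which the text does not state.
- *That settings will report different scales.* The phrase "in a global manner, according to clinical setting" allows this reading but also an overall choice. Nothing says that the optimal scale replaces the others or feeds the meta-analysis.

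**Conclusion.** The point holds in limited form. The one unconditional outcome model named in section 7.4 does not estimate the arm effect. The effect that the plan does promise has no model, effect measure, time point or covariates beyond a possible unadjusted rank test. This is so under either meaning of 'scale'.

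The risk to the false-positive rate is conditional. It arises only if outcome scales are meant, and then only for the choice between Barthel and Lawton. The ceiling is about 9% per setting instead of 5%, and about 38% over five settings instead of 23%. It rests on an assumed correlation of 0.5, an assumed two-sided 5% level, independent settings, and selection that favours the larger arm difference. If frailty tools are meant, the step belongs to the observational question and this risk does not arise.

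**What to change.** In section 7.4:

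1. State what 'scale' means. Label the scale comparison exploratory, fit it without the arm variable, and state that it does not decide which outcome is reported or pooled.
2. Prespecify one disability scale. Barthel is a reasonable choice because it is the only section 4.1 disability scale scheduled at baseline, discharge and both follow-up calls. The plan sizes the trial on disability without naming an instrument, so the sponsor should confirm which scale underlies the 40% incidence.
3. Estimate the arm effect on that scale with a model containing arm, baseline score, setting and centre, and state the effect measure and the time point.
4. Use the same scale in every setting for the section 7.3 meta-analysis.
5. Report every other section 4.1 scale whatever it shows.

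The baseline score, setting and centre are already available under the plan, so no extra data collection is needed. The cost is slightly more analysis work and a wording change, made before outcome data are analysed by arm.
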